13.4. Adverse Event and Serious Adverse Event Recording and Reporting

AEs and SAEs will be collected from signing of the ICF through completion of the end of study/early termination visit. All AEs and SAEs should be recorded in source documents; all AEs and SAEs that occur following the first dose of IMP should also be recorded in the eCRF. The investigator is required to record the AE or SAE regardless of the severity of the event or its relationship to study treatment. Prior to the first dose at the Baseline Visit/Visit 2, only AEs and SAEs related to study procedures will be recorded on the eCRF. The investigator must follow up on all AEs and SAEs reported to have occurred 30 days after study completion until the event has resolved or stabilized or at such time the investigator refers the subject to a nonstudy

physician. The investigator will document the further follow-up information in the subject's source document.

During the period specified above, the investigator will:

- Record all AEs and SAEs from the signing of the ICF through the completion of the End of Study/Early Termination visit
- Report all SAEs on an SAE Report Form to Global Pharmacovigilance.
- Report all pregnancies to Global Pharmacovigilance on the Pregnancy Surveillance Form.
- Submit any Expedited Safety Report or Suspected Unexpected Serious Adverse Reaction from Global Pharmacovigilance to the IRB/IEC.

The reporting requirements for AEs are summarized in [Table 9](#).

Table 9: Reporting Requirements for Adverse Events

Seriousness	Reporting Time	Type of Report
All Serious	Within 24 hours of first knowledge of event	Initial report on the SAE Form, appropriate eCRF, and source document
	Within 24 hours of receipt of follow-up information	Follow up report on the SAE Form, appropriate eCRF, and source document
Nonserious	Per case report form submission procedure	Appropriate eCRF and source document

Adverse Events

AEs can be reported spontaneously or elicited during open-ended questioning (ie, "How have you been feeling since your last visit?"), examination, or evaluation of a subject. Signs and symptoms must be recorded using standard medical terminology. For subjects incapable of giving consent, the legally acceptable representative may provide information regarding the subject's status.

All fields on the AE CRF page should be completed for each event with a full description of the event and date of onset/start and resolution/stop. A medical diagnosis if known, should be recorded in lieu of each individual sign and symptom associated with the diagnosis and experienced by the subject. If no medical diagnosis is known, the term used by the subject to describe the event or signs noted by the site personnel should be recorded.

Serious Adverse Events

Initial Reporting

SAEs (based on FDA/ICH definition of an SAE) require immediate reporting to Global Pharmacovigilance.

- For all SAEs, the investigator, or designee, must complete the SAE Report Form with the minimum information required by FDA and ICH and fax it to Mallinckrodt at [contact] or email at [contact] within 24 hours of first knowledge of the event even if the experience does not appear to be related to the IMP.
- The investigator, or designee, will receive acknowledgement of receipt of the SAE report form from Mallinckrodt.
- Should the investigator or designee have any difficulty in sending the SAE report, they may contact Mallinckrodt based on the information in the Study Operations Manual.
- If there is any doubt about whether the information constitutes an SAE, the information is to be treated as an SAE.

The investigator(s) or designee is required to submit the any expedited safety report or suspected unexpected serious adverse reaction to the responsible IRB/IEC.

The sponsor will ensure that any expedited safety report or suspected unexpected serious adverse reaction are submitted to the FDA and other regulatory agencies as appropriate.

Follow Up Reporting

The investigator or designee must complete an SAE report form for all follow-up information received and fax it to Mallinckrodt at [contact] within 24 hours of receipt.

The investigator(s) or designee will receive acknowledgement of receipt for each SAE report form from Mallinckrodt.

- The investigator or designee is required to provide all related information/supporting documentation of an SAE until the SAE is resolved or stabilized or the subject has been referred to a nonstudy physician for follow-up treatment.
- The investigator(s) or designee is required to submit the safety alert to the responsible IRB/IEC.
- The sponsor will ensure that any expedited safety report or suspected unexpected serious adverse reaction are submitted to the FDA and other regulatory agencies as appropriate.

13.5. Pregnancy Reporting

Certain information, although not considered an SAE, must be recorded, reported, and followed up as indicated. This includes the following:

Pregnancy exposure to an investigational medicinal product, except for exposure to prenatal vitamins. Subjects should not become pregnant during the study. If the subject becomes pregnant, study treatment must be discontinued immediately. The investigator must report the pregnancy by submitting the appropriate form to Global Pharmacovigilance (fax at [contact] or email at [contact] within 24 hours of confirmation of a pregnancy (ie, positive serum pregnancy test result). The outcome of pregnancy (eg, spontaneous abortion, live birth, still birth, congenital anomalies, birth defects) must be reported by submitting the

appropriate form to Global Pharmacovigilance (fax at [contact] or email at [contact]) within 24 hours of the pregnancy outcome being submitted to the study site. If the pregnancy results in a live birth, a postdelivery follow-up will be performed at least 28 days after the baby is born and must be reported to Global Pharmacovigilance (fax at [contact] or email at [contact]) within 24 hours of the study site becoming aware of the follow-up information. Both maternal and paternal investigational medicinal product exposures are collected.

If the female partner of a male subject becomes pregnant during the study, the site will forward the Pregnancy Notification form and the Pregnancy Report Fax cover page to Global Pharmacovigilance (fax at [contact] or email at [contact]), within 24 hours of being notified. The outcome of pregnancy (eg, spontaneous abortion, live birth, still birth, congenital anomalies, birth defects) must be reported by submitting the appropriate form to Global Pharmacovigilance (fax at [contact] or email at [contact]) within 24 hours of the pregnancy outcome being submitted to the study site. If the pregnancy results in a live birth, a postdelivery follow-up will be performed at least 28 days after the baby is born and must be reported to Mallinckrodt Pharmacovigilance (fax at [contact] or email at [contact]) within 24 hours of the study site becoming aware of the follow-up information.

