5. STUDY DESIGN

5.1. Description

This is a multicenter, multiple dose study to examine the effect of Acthar in adult subjects with FSGS who have failed to achieve remission with, or who are intolerant of, one or more previous immunosuppressive therapies. Approximately 60 subjects will be enrolled.

All enrolled subjects will be treated with Acthar 1 mL (80 U) SC 3x/week for 50 weeks. Taper to 1 mL SC 2x/week for safety and/or tolerability reasons will be allowed. If the dose is tapered to 1 mL SC 2x/week it must remain at this level for the remainder of the study. Subjects unable to tolerate 1 mL SC 2x/week will be discontinued.

All subjects will participate in the Follow-up Period at the conclusion of their participation in the study (including those who terminate early). The Follow-up Period will be 4 to 6 weeks in duration, depending on the dose of Investigational Medicinal Product (IMP).

For subjects receiving IMP 3x/week, the dose of IMP will be tapered to 2x/week for 2 weeks and then discontinued. For subjects receiving IMP 2x/week (tapered from 3x/week to 2x/week for safety), the IMP will be discontinued without a taper. All subjects, including those who terminate early, will then have an End of Study/Early Termination Visit 4 weeks after their last dose of IMP.

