8.16. End of Study/Early Termination Visit Procedures

All subjects will have an End of Study/Early Termination Visit 4 weeks after their last dose of IMP.

Subjects receiving IMP 3x/week, will have IMP tapered to 2x/week for 2 weeks at Week 50 and then discontinued. These subjects will return at Week 56 + 5 days for their End of Study Visit.

Subjects receiving IMP 2x/week will discontinue dosing without a taper. These subjects will return at Week 54 + 5 days for their End of Study Visit.

Subjects who discontinue study participation at any other time in the study will have their dose tapered to 1 mL SC 2x/week (if required) and return for the Early Termination Visit 4 weeks after their last dose of IMP.

The following assessment will be done at the End of Study/Early Termination Visit

- Current medical condition review.
- Complete physical examination.
- Vital signs, including weight.
- Clinical laboratory tests.
- Urine pregnancy test.
- Urinalysis
- IMP accountability (subjects who required taper only).
- Study diary review.
- Contact IXRS.
- AEs and concomitant medications.

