9.3. Dosing Procedures

The following Acthar treatments are to be administered. The study treatment schedule is as noted in [Table 5](#).

Table 5: IMP Treatment Schedule

Study Week	Study Period	Study Drug	Dose
Weeks 0 to 50	Open Label/Open-label Extension	Acthar	1 mL SC 3x/week ^a
Weeks 50 to 51 ^b	Follow-up Period (taper)	Acthar	1 mL SC 2x/week

^aDose can be tapered to 1 mL SC 2x/week for safety and/or tolerability reasons. If a subject ends study participation prior to Week 50, the dose of Acthar should be tapered to 1 mL SC 2x/week for 2 weeks.

^bSubjects receiving Acthar 1 mL (80 U) SC 3x/week should be tapered to 1 mL SC 2x/week for 2 weeks, with a final visit 4 weeks after the last dose of Acthar. Subjects in the open-label extension receiving 1 mL SC 2x/week at Week 49 will stop dosing at the conclusion of Week 49, with a final Visit 4 weeks after the last dose of Acthar.

The subject or subject's caregiver will administer the first dose of IMP in the clinic under the supervision of study staff. The subject will remain in the clinic for at least 1 hour post dose to monitor for allergic or anaphylactic reaction(s). After Visit 2, all doses will be administered by the subject or the subject's caregiver at home.

Throughout the trial, IMP cannot be taken on 2 consecutive days and cannot be taken more than 3 days apart, regardless of dosing frequency.

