9.3.2. Treatment Discontinuation

Treatment with Acthar should be discontinued for safety purposes if the reduction in dosing to 2x/week **and** adjustment of concomitant medications does not manage the following:

- Persistent accelerated hypertension (defined as systolic blood pressure ≥ 180 *and* diastolic blood pressure ≥ 100 mm Hg).
- Persistent edema score of 4 (see [Section 24.2](#)).
- Persistent congestive heart failure.
- Persistent diabetic signs/symptoms (ie, HbA1c $> 8\%$, or fasting plasma glucose > 126 mg/dL, or classic symptoms of hyperglycemia with random plasma glucose > 200 mg/dL).
- Any other AE of at least moderate intensity that cannot be managed with adjustment of concomitant medications.

The investigator should discontinue subjects for safety purposes any time during the study if the subject meets any of the following criteria:

- Development of unexplained and sustained (2 consecutive visits) worsening of disease defined as unresolved progression or 30% decline in eGFR from baseline, or if the subjects remains at significant risk of sequelae of nephrotic syndrome (such as serum albumin < 2.8 mg/dL) and sustained worsening of uPCR (increase $> 50\%$ from baseline).
- Development of ESRD and requirement for chronic renal replacement therapy.
- Administration of live or live-attenuated vaccines after Screening Visit/Visit 1.
- Diagnosis of a malignancy or lymphoproliferative disorder.
- Pregnancy during the course of the study.
- Development of an independent disease that requires treatment with immunosuppressive therapy or plasma exchange therapy.
- Development of a contraindication to IMP use.
- Use of any investigational drug, device, or procedure as part of a research study.

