10.6. Height and Weight

Height will be collected at screening only. Weight will be collected at specified times during the study.

10.7. Clinical Laboratory Tests, HbA1c, Serum Cystatin C, Serum Electrolytes, IGRA, Urinalysis, and Pregnancy Tests

The clinical laboratory tests are listed in [Section 24.1](#). All clinical laboratory tests will be done at a central laboratory facility except urine pregnancy (at the site) and IGRA (local laboratory). Specific instructions for collection, storage and shipment of clinical laboratory samples will be provided in a separate laboratory manual.

Samples for laboratory testing at all visits may be collected under fasted or nonfasted conditions. The date and time of the sample collection must be documented on the laboratory report. Investigators must review and sign laboratory reports. The clinical significance of each laboratory abnormality will be documented. New clinically significant laboratory abnormalities or clinically significant changes in laboratory values will be reported as AEs, as appropriate.

Hematology with differential, serum chemistry, other specific tests, and urinalysis samples will be collected at the specific times starting at screening and throughout the study.

In addition:

- All female subjects of child-bearing potential will have a serum pregnancy test at the Screening Visit/Visit 1, and a urine pregnancy test at the Baseline Visit/Visit 2 and at specified visits throughout the study. Results must be available prior to dosing with protocol mandated IMP. Subjects with positive results will be ineligible for study entry (Screening Visit/Visit 1) or withdrawn from the study. Any female subject that becomes pregnant during the study will be immediately withdrawn and the pregnancy report as per [Section 13.5](#).

If applicable, the subject's agreement to use contraception throughout their study participation, and for 4 weeks after ending study participation, will be documented.

- HBsAg and HBcAb will be performed at the Screening Visit/Visit 1. Results of these tests must be negative or nonreactive for subjects to qualify for the study.
- HCV will be performed at the Screening Visit/Visit 1. A positive HCV will automatically trigger a HCV PCR analysis. HCV PCR must be < 25 IU/mL to qualify for the study.

[REDACTED]

[REDACTED]

[REDACTED]

[REDACTED]

[REDACTED]

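### For a subject on 3x/week who becomes pregnant before Week 50, Section 13.5 requires an immediate stop while Table 5 footnote a, and Section 5.1 read with 14.1, call for two more weeks of dosing

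*Combined protocol and SAP*

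**What the plan says.** **On pregnancy.** Section 13.5 states: "If the subject becomes pregnant, study treatment must be discontinued immediately". Section 9.3.2 includes "Pregnancy during the course of the study" in its list of reasons for the investigator to discontinue a subject, and says nothing there about how dosing ends. Section 10.7 adds: "Any female subject that becomes pregnant during the study will be immediately withdrawn".

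**On ending before Week 50.** Footnote a to Table 5 (Section 9.3), whose marker sits on the 3x/week dose, says: "If a subject ends study participation prior to Week 50, the dose of Acthar should be tapered to 1 mL SC 2x/week for 2 weeks". It makes no exception by reason for stopping. Section 5.1 puts all subjects, early terminators included, into a Follow-up Period, in which those on 3x/week go down to 2x/week for two weeks before stopping. Section 14.1 requires subjects withdrawn for whatever reason to enter the follow-up period, and gives a positive pregnancy test as an example of a ground for discontinuation. Section 8.16 says that subjects who discontinue at any other time "will have their dose tapered to 1 mL SC 2x/week (if required"; the bracket closes there without saying when a taper is required.

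**On subjects already at 2x/week.** Section 5.1 says: "For subjects receiving IMP 2x/week (tapered from 3x/week to 2x/week for safety), the IMP will be discontinued without a taper". Section 8.16 says the same.

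**The concern.** A site with a newly pregnant subject on 3x/week finds one section that stops drug at once and others that, taken at their word, keep her on drug for two more weeks. I found no exemption from the taper for pregnancy and no statement of which section prevails. Whichever passage the site follows, it departs from another.

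What is at stake is first whether a pregnant subject receives further drug. Next come the records that hang on the last dose: exposure, the Early Termination Visit (4 weeks after the last dose, Sections 5.1 and 8.16), and the end of adverse event collection, which Section 13.4 ties to that visit. Severity and frequency of adverse events is a primary endpoint (Section 4.1), so the observation window of such a subject depends on which passage was followed.

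**Working it through.** **Inputs**

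- Dose per injection: 1 mL = 80 U (Sections 3.3 and 5.1).
- Taper: 2 injections a week for 2 weeks (Table 5 footnote a; Section 5.1).
- Final visit: 4 weeks after the last dose (Sections 5.1 and 8.16).
- Planned end of treatment: Week 50.

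**Step 1: reproduce the plan's own figures.** Final visit week = 50 + taper weeks + 4.

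- 3x/week at Week 50: 50 + 2 + 4 = 56.
- 2x/week at Week 50: 50 + 0 + 4 = 54.

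Both match Section 8.16 and Table 1 footnote b. The 4 to 6 week Follow-up Period in Section 5.1 follows in the same way (0 + 4 and 2 + 4). For subjects who finish the planned treatment, the taper rule is therefore coherent: 3x/week tapers, 2x/week does not.

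**Step 2: apply each rule to a subject on 3x/week found pregnant at week T, with T before 50.**

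| Rule | Further doses | Last dose | Final visit |
|---|---|---|---|
| Section 13.5, immediate stop | 0 | T | about T + 4 |
| Table 5 footnote a; Section 5.1 with 14.1 | 2 x 2 = 4 | about T + 2 | about T + 2 + 4 = T + 6 |

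Difference in dose: 4 x 80 U = 320 U. Difference in last dose and in Early Termination Visit: about 2 weeks.

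**Step 3: look for a passage that settles it.**

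- Section 9.3.2 names pregnancy but not the taper.
- Section 14.1 names a positive pregnancy test and sends withdrawn subjects into the follow-up period without exception. Table 5 labels its taper row as part of that period.
- Section 8.16 makes the early-termination taper conditional, but leaves the condition undefined.
- Section 10.7 concerns withdrawal from the study and does not time the last dose.

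None of these resolves the conflict.

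**Step 4: the same check for a subject on 2x/week.** Sections 5.1 and 8.16 give 0 further doses. Footnote a would give 4 only if it were read apart from the 3x/week dose it is attached to. A pregnant subject on 2x/week therefore meets no conflict on the natural reading.

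**Number affected.** The documents give no expected pregnancy rate. With k such subjects the total is 4k doses, or 320k U. I put no value on k. It should be small: about 60 subjects are planned, women of childbearing potential must agree to contraception (Section 6.1), and pregnancy tests are scheduled throughout (Table 1).

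**The case against.** The best defence is that Section 13.5 is specific and uses *must*, whereas footnote a is general and uses *should*, so a site would ordinarily follow 13.5. That is a sensible way to read a protocol, and it lowers the chance of a wrong step. But the protocol does not state this precedence, and Section 14.1 pulls the other way by applying the follow-up period whatever the reason for withdrawal.

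It is also fair to say that the visit and adverse event rules follow the actual last dose, so they do not themselves conflict. That stands: they move with the choice of rule and are not a second contradiction.

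Three stronger readings are tempting, and the documents do not support them.

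- *That footnote a makes every early terminator dose for two more weeks, including subjects already on 2x/week or stopped because they could not tolerate it.* The footnote is attached to the 3x/week dose, tapering to 2x/week presupposes a higher frequency, and Sections 5.1 and 8.16 both say that 2x/week subjects stop without a taper. What remains is a wording gap: the footnote does not state its own limit.
- *That the condition in Section 8.16 is arbitrary, or is overridden by Table 5.* The paragraphs just before it distinguish 3x/week from 2x/week, so it most naturally means still on 3x/week. Nothing ranks Table 5 above Section 8.16. The condition is nonetheless undefined.
- *That Section 10.7 is a second order to stop drug at once.* It orders withdrawal from the study. Only Section 13.5 times the stop of treatment.

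**Conclusion.** The contradiction is real, and it is confined to subjects on 3x/week who become pregnant before Week 50. For each such subject the difference, read literally, is 0 versus 4 further doses (320 U), with a shift of about 2 weeks in the last dose and the Early Termination Visit. This assumes that the full two-week taper would be given and that the final visit is held 4 weeks after the last dose.

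Few subjects would be affected. Analysis populations, endpoint definitions and sample size do not change; Section 12.9 reports no formal sample size calculation. The point should still be corrected, because it governs drug exposure in pregnancy and as written leaves a site unable to comply with every section.

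The missing limit in footnote a and the undefined condition in Section 8.16 are secondary wording points. A reader might infer from them a contradiction covering all early terminators, but the placement of the footnote and Sections 5.1 and 8.16 indicate otherwise.

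**What to change.** Reconcile Table 5 footnote a with Sections 5.1, 8.16, 9.3.2, 13.5 and 14.1, so that each stopping reason and each current dosing frequency leads to one instruction on how dosing ends. In particular:

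- state in one place how dosing ends in pregnancy, and refer to it from the other sections;
- state in footnote a which subjects it covers;
- replace the undefined condition in Section 8.16 with a reference to the single instruction;
- say in Section 14.1 whether entering the follow-up period always implies the taper.

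Which rule applies is a decision for the sponsor's clinical team. The cost is wording only, in an amendment or clarification letter, with no effect on data collection or sample size.

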14. SUBJECT DISCONTINUATION OR WITHDRAWAL

14.1. Subject Withdrawal

Subjects who discontinue, or are withdrawn from the study for any reason, will be required to enter the follow-up period and have the end of study/early termination safety assessments (see [Section 8.16](#)) to assess their continued well-being.

The reason for discontinuation will be recorded. A subject may be discontinued from the study for the following medical or administrative reasons:

Withdrawal by Subject

Subjects will be free to discontinue from the study at any time. Subjects who have received at least 1 dose of IMP but do not complete the study will not be replaced.

Adverse Event

If a dosed subject suffers an AE that, in the judgment of the investigator, sponsor or MM, presents an unacceptable consequence or risk to the subject, the subject will be discontinued from further participation in the study.

Death

In the event that a subject dies during the study, death will be the reason for discontinuation.

Lost to Follow-up

Every effort should be used to maintain contact with subjects during their participation in the study. A subject may be considered lost to follow-up if there is no response to 3 attempts to

reach the subject by telephone and no response to a certified letter sent to the last known address of the subject. Efforts to contact the subject should be noted in source documentation.

Met Withdrawal Criteria

If a subject develops a condition that meets any of the exclusion criteria ([Section 6.2](#)) or fails to meet an inclusion criteria ([Section 6.1](#)) during the study that is not considered to be an AE or is noncompliant (eg, has a positive pregnancy or drug screening test), the subject will be discontinued from further participation in the study. Discontinuation is also mandated for safety and/or tolerability issues as outlined in [Section 9.3.2](#)).

Other

If the above reasons are not applicable, please use the “Other” option and provide the appropriate reason for subject withdrawal.

For subjects who discontinue or are withdrawn from the study for any reason, the investigator will notify the sponsor and when possible, the subject will be required to have the early termination safety assessments ([Section 8.16](#)) to assess their continued well-being.

